2.2. Endpoints

Primary Endpoint

The primary endpoint of this study is wavefront aberrations measured at 4-meter distance (0.25 D target vergence) and near (25 cm with 4 D target vergence).

Secondary Endpoint

The secondary endpoint of this study is Off-axis refraction at both temporal and nasal fields of retina at $\pm 10^{\circ}$, $\pm 20^{\circ}$, $\pm 30^{\circ}$ with targets at 4 meters and $\pm 30^{\circ}$ only with targets at 25 cm.

Other Exploratory Endpoints and observations include:

- Corneal and test article on-eye topography
- Accommodative response with target vergence of 0.25 D, 1 D, 2 D, 3 D and 4 D
- Slit lamp findings
- LogMAR visual acuity under HLHC, LLHC, and HLLC conditions
- Lens fit assessment
- Subjective vision assessment (CLUE Vision)

2.3. Hypotheses

Primary Hypotheses:

- 1. After the 10-minute lens settling period, distance (4 meters) spherical aberration (Z_4^0) measured with RMY-100 on the eye will be similar or larger than that measured from the post-OK eyes.
- 2. After the 10-minute lens settling period, near (25 cm) spherical aberration (Z_4^0) measured with RMY-100 on the eye will be similar or larger than that measured from the post-OK eyes.

Secondary Hypotheses:

- 1. After the 10-minute lens settling period, distance (4 m) off-axis refraction at $\pm 30^{\circ}$ retinal eccentricity measured with RMY-100 on the eye will be similar or larger than that measured from the post-OK eyes.
- 2. After the 10-minute lens settling period, near (25 cm) off-axis refraction at $\pm 30^{\circ}$ retinal eccentricity measured with RMY-100 on the eye will be similar or larger than that measured from the post-OK eyes.

Other Hypotheses:

- 1. After the 10-minute lens settling period, the slope of accommodative response measured with RMY-100 on the eye will be similar as that measured from the post-OK eyes.
- 2. After the 10-minute lens settling period, distance (4 m) and near (25 cm) wavefront aberrations, off-axis refractions within $\pm 30^{\circ}$ retinal eccentricity, and the slope of accommodative response measured with RMY-100 on the eye will be different from that measured with spectacle trial lenses on eye.

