 With sphero-cylindrical correction in the spectacle trial frame with Distance target (4 m) With sphero-cylindrical correction in the spectacle trial frame with Near target (25 cm) 	
 For Control group subjects (better OK treated eye): Bare eye with Distance target (4 m) Bare eye with Near target (25 cm) 	
Note : For subjects in the Control group, their latest wavefront aberration data prior to orthokeratology treatment will also be collected, if available.	

1.13	Accommodative Response	 Collect sphero-cylindrical auto-refraction with target vergence of 0.25 D, 1 D, 2 D, 3 D and 4 D, respectively. Three repeated measurements per each target vergence: For Test group subjects (OD only): With sphero-cylindrical correction in the spectacle trial frame over the eye For Control group subjects (better OK treated eye): 	
		• Bare eye	
1.14	Off-axis Refraction	 Collect off-axis refraction with an open-field autorefractor under the following conditions, 3 repeated measures per each condition: With distance targets (4 m) at field angles of 0°, ±10°, ±20°, and ±30°; With near targets (25 cm) at field angles of ±30° only. 	
		 For Test group subjects (OD only): Bare Eye, with Distance target (4 m): 0°, ±10°, ±20°, and ±30° With sphero-cylindrical correction in the spectacle trial frame over the eye, with Distance target (4 m): ±10°, ±20°, and ±30° With sphero-cylindrical correction in the spectacle trial frame over the eye, with Near target (25 cm): ±30° For Control group subjects (better OK treated eye): 	
		For Control group subjects (better OK treated eye) :	

		 Bare Eye with Distance target (4m): ±10°, ±20°, and ±30° Bare Eye with Near target (25cm): ±30° 	
1.15	Distance	Perform monocular distance FTDRS LogMAR	
1.15	ETDDC	viewal aquity test at a 4 mater distance under the	
	LIDKS	Visual acuity lest at a 4-meter distance under me	
	LOGIMAR	following conditions with one measurement per	
	Visual Acuity	condition.	
		1. Dim illumination (e.g., <2.5 lux), low	
		luminance, with high contrast charts (LLHC);	
		2. Bright illumination (e.g., >400 lux), high	
		luminance with low contrast charts (HLLC):	
		3. Bright illumination (eg. >400 lux), high	
		huminance with high contrast charts (HLHC).	
		For Test group subjects (OD only):	
		• VA will be measured with spherical refraction	
		in the trial fame.	
		For Control subjects (better OK treated eye):	
		 VA will be measured with Bare Eye. 	
		254-00 1004 (2002) AMERICAN (2014) (214 (2014) 1007 (202)	

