14. STATISTICAL METHODS

14.1. General Considerations

All data summaries and statistical analyses will be performed using the SAS software Version 9.4 (SAS Institute, Cary, NC). Throughout the analysis of data, the results for each subject/eye will be used when available for summarization and statistical analysis. Unscheduled visits will be summarized separately and will be excluded from the statistical analysis.

Summary tables (descriptive statistics and/or frequency tables) will be provided for all baseline variables, efficacy variables and safety variables as appropriate. Continuous variables will be summarized with descriptive statistics (n, mean, standard deviation [SD], median, minimum and maximum). Frequency count and percentage of subjects or eyes within each category will be provided for categorical data.

All statistical analysis will be conducted on the per-protocol population defined in Section 14.3.

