14.5. Primary Analysis

Primary efficacy analysis:

Distance and near wavefront aberration, specifically, spherical aberration (Z_4^0), will be analyzed using a linear mixed model. Each model will include the experimental design factors: treatment, distance and treatment by distance interaction and subject as random effect. Other baseline characteristics known of importance such as age and gender will be included as fixed covariates when appropriate. Kenward and Roger method will be used for the calculation of the denominator of degrees of freedom.³⁶

Comparisons between the treatment groups will be carried out using 95% confidence intervals constructed of least-square means (LSM) differences (RMY-100 minus OK) from the linear mixed models at each distance. Statistical difference will be concluded in the lower limit is greater than 0 or the upper limit is less than 0.

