14.7. Other Exploratory Analyses

Summary statistical analysis will be provided for the following other observations:

- Corneal and test article on-eye topography
- Accommodative response with target vergence of 0.25 D, 1 D, 2 D, 3 D and 4 D
- Slit lamp findings (OD, OS)
- LogMAR visual acuity under HLHC, LLHC, and HLLC conditions (OD, OU)
- Lens fit assessment (OD, OS)
- Subjective vision assessment (CLUE Vision)

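### Two hypotheses concern the slope of accommodative response, but section 14 plans only per-vergence summaries and no slope contrast

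*Combined protocol and SAP*

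**What the plan says.** Section 2.3 of the protocol puts two statements about a slope under its Other Hypotheses. The first compares groups: "the slope of accommodative response measured with RMY-100 on the eye will be similar as that measured from the post-OK eyes". The second compares conditions within Test subjects: "the slope of accommodative response measured with RMY-100 on the eye will be different from that measured with spectacle trial lenses on eye".

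The endpoint in section 2.2 is not a slope. It is listed as "Accommodative response with target vergence of 0.25 D, 1 D, 2 D, 3 D and 4 D", and section 14.7 repeats that item under the lead-in "Summary statistical analysis will be provided for the following other observations". Section 14.1 says what such a summary contains: "Continuous variables will be summarized with descriptive statistics (n, mean, standard deviation [SD], median, minimum and maximum".

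The raw data come from section 7.2. At Visit 1 the site is told: "Collect sphero-cylindrical auto-refraction with target vergence of 0.25 D, 1 D, 2 D, 3 D and 4 D, respectively", with "Three repeated measurements per each target vergence". Test eyes are measured with the spectacle correction in the trial frame and Control eyes bare. At Visit 2 the same five vergences are measured three times each with RMY-100 on the eye.

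Between-group contrasts with 95% confidence intervals appear in two places only. Section 14.5 has intervals "constructed of least-square means (LSM) differences (RMY-100 minus OK) from the linear mixed models at each distance" for spherical aberration, and section 14.6 does the same for off-axis refraction at ±30°. Neither covers accommodation.

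**The concern.** The stated hypotheses and the stated analysis are about different quantities. The hypotheses concern one derived number per eye and condition, the slope of response on target vergence. The analysis tabulates five separate levels. In the readable text the word *slope* occurs only in section 2.3. Section 14 has no step that forms a slope and none that compares slopes.

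Two other sections make this more than missing detail. Section 4.2 says accommodative responses will be compared with those of orthokeratology eyes, but 14.7 plans no comparison. Section 14.2 says the data will serve to design future trials. For a trial with this outcome, that needs the between-subject SD of the slope, which the planned table does not give. If a slope contrast is added later, it becomes a change to report under section 14.10, chosen in a non-masked study after the data can be seen.

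**Working it through.** The documents give no power, SD, effect size or margin for this endpoint, so there is no figure of the plan's own to reproduce. The check asks what the planned table can and cannot yield.

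**Inputs.** Target vergences x = 0.25, 1, 2, 3, 4 D (2.2). Three readings at each, so 5 × 3 = 15 per eye and condition (7.2). Minimum completers: 20 Test and 15 Control (4.3). SDs and correlations below are assumptions.

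**1. Mean slope from the tabulated means.**
- Mean of x = 10.25/5 = 2.05.
- Sxx = 1.80² + 1.05² + 0.05² + 0.95² + 1.95² = 9.05.
- The least-squares slope is Σ wᵢyᵢ with wᵢ = (xᵢ − 2.05)/9.05. The weights are −0.199, −0.116, −0.006, 0.105 and 0.215.
- The slope is linear in the five values. With complete data, the mean slope of a condition is therefore the same weighted sum of its five tabulated means, and a point difference between conditions follows.

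**2. SD of the slope.** This needs the covariances between vergences within subjects, and 14.7 does not report them. For a common SD s at each vergence and equal correlation ρ, the weights sum to zero, so slope SD = s × √((1 − ρ)/9.05).

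| Assumed ρ | Slope SD |
|---|---|
| 0 | 0.33s |
| 0.5 | 0.24s |
| 0.8 | 0.15s |
| 0.9 | 0.11s |

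The same table of means and SDs is compatible with slope SDs that differ threefold, so no confidence interval can be recovered from it.

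**3. What a planned contrast would give.**
- 95% half-width = t(0.975, n₁ + n₂ − 2) × √(1/n₁ + 1/n₂) × slope SD.
- For 20 versus 15: √(1/20 + 1/15) = 0.342, and the half-width is 0.69 slope SDs.
- For 25 versus 20 (all enrolled): √(1/25 + 1/20) = 0.300, and the half-width is 0.61 slope SDs.
- For an assumed slope SD of 0.10 to 0.30 D/D, the 20 versus 15 half-width is ±0.07 to ±0.21 D/D.

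**4. Could it show similarity?** Two one-sided tests at 5% each, with 20 versus 15, a true difference of zero and a normal approximation, have about 0% power for a margin of 0.5 slope SD and 80% for a margin of 1 slope SD. The plan sets no margin.

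**5. Residual refractive error.**
- The autorefractor reads the total refractive state of the eye. An eye 0.50 D myopic that follows the target with gain k accommodates less, so its reading shifts by about (1 − k) × 0.50 D. At an assumed k = 0.8 that is 0.10 D; at k = 1 it is zero.
- At the 0.25 D target such an eye cannot relax below 0.50 D. Ideal readings become 0.50, 1, 2, 3, 4, and the slope moves from 1.00 to 1.00 − 0.199 × 0.25 = 0.95.
- Without the 0.25 D point, Sxx = 1.5² + 0.5² + 0.5² + 1.5² = 5.0. Under the assumptions of step 2 the slope SD grows by √(9.05/5.0) = 1.35.

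**The case against.** The strongest defence is that descriptive handling is a legitimate choice here. The hypotheses are the third tier of a study that calls itself exploratory and is not powered. The raw autorefractor files are exported and kept (15.1), so a slope can be computed at any time, and section 14.10 allows documented changes. That stands, and it limits the weight of the point. It does not make the analysis match the hypotheses.

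A second defence is that the Appendix D work aid on the open-field autorefractor is not readable and may define how a response or a slope is derived. That also stands. What is established is only that section 14 contains no slope contrast.

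Three stronger readings are tempting, and the documents do not support them:

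- **The hypotheses cannot be answered at all.** The limitation is in the planned output, not in the data, and even that output yields mean slopes when the data are complete (step 1).
- **The readings go unused.** Section 14.7 summarises all five vergences. The readings are just not used for the slope hypotheses.
- **Residual myopia adds a fixed 0.50 D at every vergence and leaves the slope untouched, so the per-vergence table misleads.** Step 5 shows otherwise: the shift is smaller where the eye tracks, and flooring at 0.25 D can move the slope.

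Finally, a difference with a confidence interval does not prove similarity. That is correct, and the added estimates should be labelled accordingly.

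**Conclusion.** The point holds as a mismatch between hypothesis and analysis. Section 2.3 makes two statements about a slope, and section 14 yields neither a slope SD nor a confidence interval for a slope difference. The loss is precision information: slope SDs from 0.11s to 0.33s fit the same table, if SDs and correlations are equal across vergences.

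The importance is small. These are Other hypotheses in a pilot, and the primary and secondary analyses are unaffected. Even with the contrast added, the between-group interval of about ±0.69 slope SDs is an estimate to inform later work and cannot confirm that the slopes are similar.

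**What to change.** Amend section 14.7 before database lock:

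1. For each eye and condition, convert the three readings at each vergence to spherical equivalent and average them. State the sign convention that turns this into a response.
2. Fit a least-squares line of response on target vergence over the five vergences and take its slope. Alternatively, use a mixed model with condition, vergence, their interaction, and random subject intercept and slope.
3. Report the mean and SD of the slope for RMY-100, post-OK and spectacle trial lenses.
4. Report the RMY-100 minus OK slope difference with its 95% CI (Other Hypothesis 1), and the paired RMY-100 minus spectacle difference with its 95% CI (the slope part of Other Hypothesis 2).
5. Label both as exploratory estimates that do not demonstrate similarity, since no margin is set.
6. Add a sensitivity fit without the 0.25 D point. Post-OK eyes are measured bare, and inclusion criteria 7 to 9 apply to their pre-treatment status, so residual myopia could floor that reading.

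Keep the per-vergence table as descriptive support. If the sponsor prefers not to add contrasts, the alternative is to reword the slope statements in 2.3 as descriptive aims.

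The cost is a paragraph of wording and a short derivation on data already collected, with no new visits or measurements. The downside is one or two more exploratory estimates to report in a plan that makes no multiplicity adjustment.

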3. TARGETED STUDY POPULATION

3.1. General Characteristics

Healthy male and female subjects between ages of 7 and 25 years (inclusive) with best sphererefraction between -1.00 D to -5.00 D (inclusive) and 1.00 D or less astigmatism will be recruited. Subjects must have healthy eyes and satisfy all the eligibility criteria at enrollment. There are no restrictions as to gender or race/ethnicity. Subjects may be neophytes or current soft contact lens wearers.

3.2. Inclusion Criteria

Potential subjects must satisfy all of the following criteria to be enrolled in the study:

Inclusion Criteria after Screening:

- 1. Pediatric subjects (<18 years old) must read (or be read to), understand, and sign the Statement of Information and Assent and receive a fully executed copy of the form.
- 2. Adult subjects (≥18 years old) and parent(s) or legal guardian(s) of pediatric subjects must read, understand and sign the Statement of Informed Consent and receive a fully executed copy of the form.
- 3. Appear able and willing to adhere to the instructions set forth in this clinical protocol.
- 4. Between 7 and 25 years of age (inclusive).
- 5. Have normal eyes (i.e., no ocular medications or infections of any type).

Below inclusion criterion is for subjects to be enrolled to the Control group only:

6. Are existing orthokeratology patients whose current treatment has been stabilized for at least 1 months and with complete pre-treatment record, e.g., spherocylindrical refraction and corneal topography. Pre-treatment wavefront aberration measures are preferred by not required.

Inclusion Criteria after Baseline (apply to subjects to be enrolled to the Test group and to Control group subjects regarding their pre-OK treatment):

- 7. Vertex-corrected distance subjective best-sphere refraction must be between -1.00 D and -5.00 D (inclusive) in each eye.
- 8. Cylindrical refraction must be 1.00 D or less in each eye, by subjective sphero-cylindrical refraction.
- 9. Have sphero-cylindrical best-corrected visual acuity of 20/25 or better in each eye.

3.3. Exclusion Criteria

Potential subjects who meet any of the following criteria will be excluded from participating in the study:

Exclusion Criteria after Screening:

- 1. Currently pregnant or lactating.
- 2. Any systemic allergies, infectious disease (e.g., hepatitis, tuberculosis), autoimmune disease (e.g., rheumatoid arthritis), or other diseases, by self-report, which are known to interfere with contact lens wear and/or participation in the study.
- 3. Use of systemic medications (e.g., chronic steroid use) that are known to interfere with contact lens wear and/or participation in the study.
- 4. Any current use of ocular topical medication (occasional use of re-wetting drops is allowed).
- 5. Any previous or planned ocular or intraocular surgery, including refractive surgery.
- 6. Participation in any contact lens or lens care product clinical trial within 7 days prior to study enrollment.
- 7. Employee or their children/relatives of investigational clinic (e.g., Investigator, Coordinator, Technician).

Below exclusion criteria are for subjects to be enrolled to the Test group only

- 8. Current or recent (within 30 days from enrollment) rigid lens wearers.
- 9. History of orthokeratology treatment.

Exclusion Criteria after Baseline:

- 10. Any ocular allergies, infections or other ocular abnormalities that are known to interfere with contact lens wear and/or participation in the study. This may include, but not be limited to, aphakia, uveitis, ocular hypertension, glaucoma, severe keratoconjunctivitis sicca, history of recurrent corneal erosions, keratoconus, keratoconus suspect, pellucid marginal degeneration, entropion, ectropion, extrusions, chalazia, and recurrent styes.
- 11. Any Grade 3 or greater slit lamp findings (eg, edema, corneal neovascularization, corneal staining, tarsal abnormalities, and conjunctival injection) on the FDA scale.
- 12. Any ocular abnormality that is contraindicated contact lens wear.
- 13. Any corneal scar within central 5mm
- 14. Binocular vision abnormality, intermittent strabismus or strabismus.

Below exclusion criteria are for subjects to be enrolled to the Test group only

15. Any corneal distortion resulting from ocular diseases or previous hard or rigid gas permeable contact lens wear.

3.4. Enrollment Strategy

Study subjects will be recruited from the Institution/clinical site's subject database and/or utilizing Independent Ethics Committee (IEC) or Institutional Review Board (IRB) approved materials.

In addition, the Control group subjects will be recruited through referrals from the university optometry clinic and independent Eye Care Professionals (ECPs) who will identify potential

subjects by reviewing the case history of existing orthokeratology treated patients in their practices.

It is anticipated that the age distribution is likely to be different between the two study groups, e.g., orthokeratology patients may be of younger age than soft contact lens patients. Therefore, the study site is encouraged to recruit subjects in each study group with similar age, gender and baseline refraction distributions. Specifically, the site will aim to enroll approximately 15 subjects in the Test group who match the subjects enrolled in the Control group with regard to age, gender and baseline refraction as much as possible. The clinical site is encouraged to enroll subjects between 7 and 15 years of age, if available within the enrollment timeline.

4. STUDY DESIGN AND RATIONALE

4.1. Description of Study Design

This is a two-arm parallel, non-masked, bilateral, non-dispensing study with one Test arm and one concurrent, non-randomized Control arm.

For subjects enrolled in the Test arm, investigational test articles will be bilaterally fitted to the subject's eyes. Concurrently, a smaller sample of subjects who are established orthokeratology lens wearers will be enrolled to Control arm. Endpoint measures will be collected over one eye only (Test arm: OD only; Control arm: better OK fitted eyes, eg, better centration and better myopia correction outcome, etc., based on the investigator's judgement. If both eyes are treated equally well, choose OD).

For subjects in the Test arm, there will be a total of 2 visits: Visit 1: Screening, baseline endpoint measures with bare eye/spectacle trial lenses Visit 2: Lens fitting, endpoint measures over the study lenses and final evaluation.

For the Control arm, the investigators will pre-identify subjects through reviewing the case history of existing orthokeratology treated patients. Only subjects with complete pre-treatment record, e.g., spherocylindrical refraction and corneal topography will be invited to participate in the study.

For subjects in the Control arm, there will be a total of 1 visit: Visit 1: Screening, baseline and endpoint measures over the selected eyes.

Study participants will have no access to test articles at study closure.

4.2. Study Design Rationale

The study was designed to evaluate the on-eye optical performance of the RMY-100 lens. The RMY-100 lens was designed to have an optical profile that simulates the optical effect of an orthokeratology lens on the eye. As such optical characteristics and effects of RMY-100 lens on the eye, including wavefront aberrations, especially spherical aberration, lens-on-eye

topography, accommodative responses and off-axis refraction, will be measured and compared with those measured from eyes of patients of current orthokeratology treatment.

Due to the two populations to be investigated are different, ie., non-OK patients that will be fit with soft contact lenses and current over-night OK patients with no vison correction during the day, the study is designed to be a non-randomized, two-arm parallel, non-masked study.

4.3. Enrollment Target and Study Duration

Approximately 25 subjects will be enrolled in the Test arm of the study with a minimum of 20 subjects targeted to complete the study.

Approximately 20 subjects will be enrolled in the Control arm of the study with a minimum of 15 subjects targeted to complete the study.

The study will be conducted at one clinical site.

The total duration of the study enrollment will be approximately 10 weeks, unless otherwise approved by the Sponsor. The total duration of the study is expected to be 14 weeks (including the enrollment period).

